6.6. Appendix 6: Searching Criteria for Special Safety Topics

Abuse Liability

To identify AE terms suggestive of potential abuse liability, narrow terms from SMQ of Drug abuse and dependence (20000101) will be used.

Acute Gallbladder Disease

All biliary colic, cholecystitis, or other suspected events related to gallbladder disease will be identified using the MedDRA PTs in any of the following:

- Narrow PTs in Gallbladder related disorders SMQ (20000124)
- Narrow PTs in Biliary tract disorders SMQ (20000125)
- Narrow PTs in Gallstone related disorders SMQ (20000127).

Amputation/Peripheral Revascularization

Amputations/peripheral revascularization events will be identified using the following MedDRA PTs:

- Amputation
- Peripheral revascularization.

C-cell Hyperplasia and Thyroid Malignancies

Thyroid malignancies and C-Cell hyperplasia will be identified using MedDRA HLT for Thyroid neoplasms and PT for thyroid C-cell hyperplasia.

Diabetic Retinopathy Complications (preferred terms)

Arteriosclerotic retinopathy, Blindness, Choroidal neovascularisation, Cystoid macular oedema, Detachment of macular retinal pigment epithelium, Detachment of retinal pigment epithelium, Diabetic blindness, Diabetic eye disease, Diabetic retinal oedema, Diabetic retinopathy, Diabetic uveitis, Exudative retinopathy, Eye laser surgery, Fundoscopy, Fundoscopy abnormal, Intra-ocular injection, Macular detachment, Macular oedema, Maculopathy, Noninfective chorioretinitis, Noninfective retinitis, Phacotrabeculectomy, Retinal aneurysm, Retinal arteriovenous malformation, Retinal artery embolism, Retinal artery occlusion, Retinal artery stenosis, Retinal collateral vessels, Retinal cryoablation, Retinal detachment, Retinal exudates, Retinal haemorrhage, Retinal laser coagulation, Retinal neovascularisation, Retinal oedema, Retinal operation, Retinal thickening, Retinal vascular disorder, Retinal vascular occlusion, Retinal vein occlusion, Retinitis, Retinopathy, Retinopathy haemorrhagic, Retinopathy hypertensive, Retinopathy hyperviscosity, Retinopathy proliferative, Venous stasis retinopathy, Vitrectomy, Scintillating scotoma, Vision blurred, Visual impairment, Blindness transient, Blindness unilateral, Sudden visual loss, Visual acuity reduced, Visual acuity reduced transiently, Diplopia, Amaurosis, Amaurosis fugax

Note: This table was developed for MedDRA version 25.0 and will be updated to the version of MedDRA to be used at the time of the final database lock.

Hepatic Events

Treatment-emergent potentially drug-related hepatic events will be identified using the MedDRA PTs contained in any of the following:

- Broad and narrow terms in the Liver related investigations, signs and symptoms SMQ (20000008)
- Broad and narrow terms in the Cholestasis and jaundice of hepatic origin SMQ (20000009)
- Broad and narrow terms in the Hepatitis non-infections SMQ (20000010)

- Broad and narrow terms in the Hepatic failure, fibrosis and cirrhosis and other liver damage SMQ (20000013)
- Narrow terms in the Liver-related coagulation and bleeding disturbances SMQ (20000015).

Hypersensitivity Reactions

Treatment-emergent hypersensitivity reactions will be identified based on the following:

- Narrow and algorithm terms in Anaphylactic reaction SMQ (20000021)
- Narrow terms in Angioedema SMQ (20000024)
- Narrow terms in Severe cutaneous adverse reactions SMQ (20000020)
- Narrow terms in Hypersensitivity SMQ (20000214).
- Narrow terms in Vasculitis SMQ (20000174).

For the Anaphylactic reaction SMQ, each term is classified by scope (Narrow, Broad) and by category (A, B, C, D). All Narrow terms are category A, and all Broad terms are category B, C, or D. In addition to the usual Narrow and Broad searches, the SMQ defines an algorithm to further refine the cases of interest. For Time Period A of potential immediate hypersensitivity analysis, the Anaphylactic reaction SMQ algorithm will be included. The algorithm is based upon events that occur within Time Period A. The counts and percentages of participants who experienced a TEAE for the following will be analyzed for each of Time Period A and Time Period B (potential non-immediate hypersensitivity analysis):

- any narrow term from any one of the 4 SMQs indicated above (that is, combined search across narrow of all 5 SMQs)
- any narrow scope term within each SMQ, separately (that is, narrow SMQ search). For analysis in Time Period A, any term from Anaphylactic reaction SMQ algorithm.

Injection Site Reactions

The ISR AE will be identified using the MedDRA PT in any of the following:

- HLT of Injection site reaction
- HLT of Administration site reaction
- HLT of Infusion Site Reactions

Pancreatitis Events

Determination of investigator-reported events will be through the “Acute pancreatitis” MedDRA SMQ (20000022, narrow scope) and a “Chronic pancreatitis” PT search of the AE database, while adjudication-confirmed pancreatitis are found from adjudication forms.

Malignancy

The malignancy events will be identified using the MedDRA PT contained in Malignant tumours SMQ (20000194) narrow scope or Tumours of unspecified malignancy SMQ (20000195) narrow scope.

Major Depressive Disorder/Suicidal Ideation

AEs will be searched using MedDRA PTs from SMQs narrow scope: 20000037 (Suicide/self-injury) and 20000167 (Depression [excluding suicide and self injury]).

Metabolic Acidosis, Including Diabetic Ketoacidosis

Metabolic acidosis including diabetic ketoacidosis will be identified using the following MedDRA PTs:

- Diabetic ketoacidosis
- Ketoacidosis
- Euglycaemic diabetic ketoacidosis
- Ketonuria
- Diabetic ketosis
- Diabetic ketoacidotic hyperglycaemic coma
- Ketosis
- Lactic acidosis
- Urine ketone body present
- Blood ketone body
- Blood ketone body increased
- Urine ketone body, and
- Blood ketone body present.

Arrhythmias and Cardiac Conduction Disorders

The arrhythmias and cardiac conduction disorders events will be identified using the MedDRA PT contained in any of the following SMQs:

- Arrhythmias:
 - For symptoms: Arrhythmia related investigations, signs and symptoms SMQ (20000051), narrow and broad terms
 - For supraventricular arrhythmias: In Cardiac arrhythmia SMQ, under tachyarrhythmia sub SMQ
 - Supraventricular tachyarrhythmia SMQ (20000057), broad and narrow terms
 - Tachyarrhythmia terms, nonspecific SMQ (20000164), narrow terms only; and
 - Ventricular tachyarrhythmia SMQ (20000058), narrow terms only.

- Cardiac Conduction Disorders
 - Conduction defects SMQ (20000056), narrow terms only; and
 - Cardiac conduction disorders High Level Term (HLT; 10000032), all PTs.

7. References

- [ADA] American Diabetes Association. 6. Glycemic targets: standards of medical care in diabetes-2020. *Diabetes Care*. 2020;43(suppl 1):S66–S76. <https://doi.org/10.2337/dc20-S006>
- [ICH] International Council for Harmonisation. Addendum on estimands and sensitivity analysis in clinical trials. To the guideline principles for clinical trials E9(R1): guidance for industry. November 2019. Accessed August 31, 2022. https://www.gmp-compliance.org/files/guidemgr/E9-R1_Step4_Guideline_2019_1203.pdf

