8.3.2.4. Calcitonin Measurements

If an increased calcitonin value (see definitions below) is observed in a participant who has been administered a medication that is known to increase serum calcitonin, then this medication should be stopped, and calcitonin levels should be measured after an appropriate washout period.

For participants who require additional endocrine assessment because of increased calcitonin concentration as defined in this section, data from the follow-up assessment will be collected in the specific section of the eCRF.

Calcitonin Measurements in Participants with eGFR ≥ 60 mL/min/1.73 m²

A significant increase in calcitonin for participants with eGFR ≥ 60 mL/min/1.73 m² is defined below. If a participant's laboratory results meet these criteria, these clinically significant laboratory results should be recorded as an AE.

- *Serum calcitonin value ≥ 20 ng/L and < 35 ng/L AND $\geq 50\%$ increase from the screening value.* These participants will be asked to repeat the measurement within 1 month. If this repeat value is increasing ($\geq 10\%$ increase), the study drug should be stopped, and the participant encouraged to undergo additional endocrine assessment and longer term, follow-up by an endocrinologist to exclude any serious adverse effect on the thyroid.
- *Serum calcitonin value ≥ 35 ng/L AND $\geq 50\%$ over the screening value.* In these participants, study drug should be stopped, and the participant recommended to immediately undergo additional endocrine assessments and longer term, follow-up by an endocrinologist.

Calcitonin Measurement in Participants with eGFR < 60 mL/min/1.73 m²

A significant increase in calcitonin for participants with eGFR < 60 mL/min/1.73 m² is defined as a *serum calcitonin value ≥ 35 ng/L AND $\geq 50\%$ over the screening value.* If a participant's labs meet these criteria, these clinically significant labs should be recorded as an AE.

In these participants, study drug should be discontinued (after first confirming the value) and the participant recommended to immediately undergo additional endocrine assessments and longer-term follow-up by an endocrinologist to exclude any serious adverse effect on the thyroid.

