9.4.4.3. Special Safety Topics

This section includes areas of interest whether due to observed safety findings, potential findings based on drug class, or agreed upon consultation with regulatory agencies for the reasons previously mentioned.

The following AEs are AEs of special interest (AESIs) for this study:

- Severe hypoglycemia
- Major adverse cardiovascular events (adjudicated). Includes, but not limited to cardiovascular death, nonfatal myocardial infarction, nonfatal stroke, and hospitalization for heart failure
- TE Supraventricular arrhythmias and Cardiac Conduction Disorders
- Hepatobiliary disorders. Includes biliary colic, cholecystitis, and other gallbladder disease
- Severe GI events
- Acute renal events
- MDD/Suicidal Behavior and Ideation
- Pancreatitis (adjudicated)
- C-Cell Hyperplasia and thyroid malignancies
- Allergic/Hypersensitivity Reactions. Includes injection site reactions and ADA formation
- Diabetic retinopathy complications
- Metabolic acidosis, including diabetic ketoacidosis
- Amputation/peripheral revascularization.

Summaries and analyses for incidence of AESIs will be provided by treatment. The details of analysis of AESI will be provided in SAP.

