4.6.5.12.2. C-Cell Hyperplasia and Thyroid Malignancies

Treatment-emergent thyroid malignancies and C-Cell hyperplasia will be considered AESIs. Detailed searching criteria can be found in Appendix 6.6 (Section 6.6).

The counts and percentages of participants with treatment-emergent thyroid C-cell hyperplasia and malignancies will be summarized by treatment and PT ordered with decreasing frequency. In addition, a listing of participants with treatment-emergent thyroid C-cell hyperplasia and neoplasms may be provided if deemed necessary.

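### The thyroid AESI is named as malignancies and C-cell hyperplasia, but SAP 6.6 searches for it with the whole thyroid neoplasms HLT, so non-malignant neoplasms can enter its total

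*SAP*

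**What the plan says.** **Thyroid.** Protocol 9.4.4.3 lists "C-Cell Hyperplasia and thyroid malignancies" among the AESIs. SAP 4.6.5.12.2 agrees: "Treatment-emergent thyroid malignancies and C-Cell hyperplasia will be considered AESIs". It plans counts by treatment and PT, and adds that "a listing of participants with treatment-emergent thyroid C-cell hyperplasia and neoplasms may be provided if deemed necessary". The search rule is in SAP 6.6: "Thyroid malignancies and C-Cell hyperplasia will be identified using MedDRA HLT for Thyroid neoplasms and PT for thyroid C-cell hyperplasia".

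**General malignancy.** SAP 4.6.5.10 makes treatment-emergent malignancy an AESI of its own. SAP 6.6 searches for it with two SMQs at narrow scope, 20000194 (malignant tumours) and 20000195 (tumours of unspecified malignancy).

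**Arrhythmia.** The AESI in Protocol 9.4.4.3 is "TE Supraventricular arrhythmias and Cardiac Conduction Disorders". SAP 4.6.5.13 instead makes every arrhythmia or conduction disorder an AESI if it is severe or serious, and tabulates these events by PT within SMQ. SAP 6.6 has a bullet that reads "For supraventricular arrhythmias: In Cardiac arrhythmia SMQ, under tachyarrhythmia sub SMQ". Under it stand SMQ 20000057 (supraventricular), SMQ 20000164 (nonspecific) and "Ventricular tachyarrhythmia SMQ (20000058), narrow terms only".

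**The concern.** A neoplasm need not be malignant. If the HLT holds non-malignant terms, as its name suggests, the table titled thyroid malignancies will count them. Three features make this more than wording.

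- Several other AESIs in this SAP, such as the hepatic, renal and arrhythmia ones, are limited to severe or serious events. The thyroid AESI is not, so a mild non-malignant finding would count in full.
- The SAP has two AESIs that both cover thyroid malignancy, with different searches. One report could show two different numbers of thyroid malignancies.
- Protocol 8.3.2.4 sends participants with a defined calcitonin rise for further work-up ("the participant encouraged to undergo additional endocrine assessment"), and Protocol 8.3.2.3 explains that calcitonin is measured because tirzepatide might affect C-cells. If calcitonin rises differed by arm, incidental findings could differ too. This is a possible route to imbalance. The documents do not show that it occurs.

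The arrhythmia listing raises a smaller question: whether ventricular events are counted in an AESI to which they do not belong.

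**Working it through.** No power, rate or effect figure bears on this point, and the plan states none to reproduce. The check is to set each AESI as named against its search.

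**Thyroid.** The table takes the HLT and the SMQs to hold what their names say. The documents do not list their contents.

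| Type of thyroid event | In the AESI as named? | Caught by the thyroid search? | Caught by the general malignancy search? |
|---|---|---|---|
| Malignant neoplasm | Yes | Yes, by the HLT | Yes, by 20000194 |
| Neoplasm of unspecified malignancy | Not stated, but inside the SAP's general malignancy AESI | Yes, by the HLT | Yes, by 20000195 |
| Non-malignant neoplasm | No | Yes, by the HLT | No |
| C-cell hyperplasia | Yes | Yes, by its own PT | Not stated |

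The third row is the defect: such an event is outside the AESI as named, inside the thyroid search and outside the malignancy search.

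In one arm, let m be the participants with a malignant or unspecified thyroid neoplasm, c the further participants with C-cell hyperplasia, and b the participants whose only thyroid event is a non-malignant neoplasm. The search gives m + c + b. The intended count is m + c. The excess is (m + c + b) - (m + c) = b. The documents give no value for m, c or b, so b can be anything from zero upwards and no inflation factor can be derived.

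SAP 4.6.5.12.2 itself uses both words: its count is titled malignancies and its optional listing covers neoplasms. The text does not settle which was meant.

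**Arrhythmia.**

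1. By the protocol's AESI name, a ventricular tachyarrhythmia is outside the AESI.
2. By the SAP's definition in 4.6.5.13, a severe or serious one is inside, because no supraventricular limit is set. The opening line of the arrhythmia search in SAP 6.6 has the same wide scope.
3. The display is by PT within SMQ, so ventricular events appear under SMQ 20000058 and supraventricular events under 20000057. The supraventricular row is not diluted.
4. The sub-heading in SAP 6.6 is therefore too narrow for two of the three SMQs under it, but the AESI count agrees with the SAP's own definition.
5. Between protocol and SAP the AESI changed twice: the SAP drops the supraventricular limit and adds a severe/serious condition. SAP 4.9, which records changes to protocol-planned analyses, mentions neither change.

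**The case against.** The strongest reply on the thyroid search is that nothing is hidden. Counts are shown by PT, so a benign term would be visible as such. Malignant thyroid PTs should also appear in the general malignancy table, Protocol 8.3.2.3 has thyroid malignancies captured in specific eCRFs, and the SAP's listing openly says neoplasms. The presence of benign terms in the HLT is an inference from its name. All of this stands, and it limits the harm: a reader who looks at the PT rows would not be misled. It does not repair the AESI total, which would still include events that its title excludes and could differ from the malignancy AESI.

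On arrhythmia, Protocol 9.4.4.3 leaves the details of AESI analysis to the SAP, so a wider SAP scope is allowed. That also stands. What remains is the wrong sub-heading and an unrecorded change of scope.

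A reader might infer more: that both AESI counts are wrong, that a false thyroid cancer signal is likely, or that a real supraventricular signal would be masked. The documents do not support these readings. They give no event rates and no rate of calcitonin-triggered work-up by arm, the arrhythmia count matches SAP 4.6.5.13, and the SMQ-level display keeps supraventricular events apart.

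**Conclusion.** The point holds for the thyroid AESI as a mismatch between name and search: as written, the search is wider than the AESI, and nothing filters the result by malignancy, severity or seriousness. The over-count equals the number of participants whose only thyroid event is a non-malignant neoplasm. That number is unknown and may be zero. The conclusion rests on one assumption, that the HLT contains at least one non-malignant term.

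The arrhythmia part is editorial: a mislabelled sub-heading, and a difference in AESI scope between protocol and SAP that SAP 4.9 does not record. No efficacy result is affected by either part. The thyroid search is worth correcting because it concerns a named safety topic and the SAP already uses the terms needed.

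**What to change.** **Thyroid, SAP 6.6.** Count as the thyroid AESI only those PTs of the thyroid neoplasms HLT that are also in SMQ 20000194 or SMQ 20000195 (both narrow), plus the PT for thyroid C-cell hyperplasia. Show the remaining thyroid neoplasm PTs in a separate row labelled non-AESI. Keep 20000195 in: with 20000194 alone, the thyroid AESI would be narrower than the SAP's own malignancy AESI, and a thyroid tumour of unspecified malignancy would be an AESI in one table and not in the other. Align the wording of the optional listing in SAP 4.6.5.12.2 with this split.

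**Arrhythmia, SAP 6.6, 4.6.5.13 and 4.9.** Move SMQs 20000058 and 20000164 out of the supraventricular sub-heading to headings of their own. Reconcile the AESI scope in Protocol 9.4.4.3 with that in SAP 4.6.5.13, and record the change in SAP 4.9.

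**Cost.** A few lines of SAP text and search programming, and one extra table row for thyroid. No new data are needed.

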10.4.1. Definition of AE

AE Definition

 An AE is any untoward medical occurrence in a participant administered a pharmaceutical product and which does not necessarily have a causal relationship with the study intervention. An AE can therefore be any unfavourable and unintended sign (including an abnormal laboratory finding), symptom, or disease (new or exacerbated) temporally associated with the use of a medicinal (investigational) product, whether or not related to the medicinal (investigational) product.

Events Meeting the AE Definition

 Any abnormal laboratory test results (hematology, clinical chemistry, or urinalysis) or other safety assessments (for example, ECG, radiological scans, vital signs measurements), including those that worsen from baseline, considered clinically significant in the medical and scientific judgment of the investigator (that is, not related to progression of underlying disease). Exacerbation of a chronic or intermittent pre-existing condition including either an increase in frequency and/or intensity of the condition. New conditions detected or diagnosed after study intervention administration even though they may have been present before the start of the study. Signs, symptoms, or the clinical sequelae of a suspected drug-drug interaction. Signs, symptoms, or the clinical sequelae of a suspected overdose of either study intervention or a concomitant medication. “Lack of efficacy” or “failure of expected pharmacological action” per se will not be reported as an AE or SAE. Such instances will be captured in the efficacy assessments. However, the signs, symptoms, and/or clinical sequelae resulting from lack of efficacy will be reported as AE or SAE if they fulfill the definition of an AE or SAE.

Events NOT Meeting the AE Definition

 Any clinically significant abnormal laboratory findings or other abnormal safety assessments which are associated with the underlying disease, unless judged by the investigator to be more severe than expected for the participant’s condition. The disease/disorder being studied or expected progression, signs, or symptoms of the disease/disorder being studied, unless more severe than expected for the

- participant’s condition.
- Medical or surgical procedure (for example, endoscopy, appendectomy): the condition that leads to the procedure is the AE.

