4.6.5.17. Diabetic Retinopathy Complications

Results of the baseline dilated fundoscopic exam will be summarized by treatment. Any TEAE suspected of worsening retinopathy triggers a follow-up dilated fundoscopic exam. A summary of TEAEs suspected of worsening retinopathy (Section 6.6) and a summary of the results of the follow-up dilated fundoscopic exam will be summarized by treatment and PT. The cases with repeated fundoscopy during the course of the trial, based on clinical suspicion of worsening retinopathy that have either findings of de novo retinopathy or progression of retinopathy, and severe/serious adverse events from the PTs defined in searching criteria in Appendix 6.6 (Section 6.6) will be considered as AESI and summarized.

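### The preferred-term list for diabetic retinopathy complications (SAP 6.6) has no vitreous haemorrhage term, so the list-based summary, and possibly the AESI count, can miss such an event

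*SAP*

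**What the plan says.** Protocol 9.4.4.3 names diabetic retinopathy complications as an adverse event of special interest (AESI). SAP 6.6 sets the search for this topic as a fixed list of MedDRA preferred terms. Part of it reads "Retinal exudates, Retinal haemorrhage, Retinal laser coagulation", another part "Eye laser surgery, Fundoscopy, Fundoscopy abnormal, Intra-ocular injection", and a third "Retinopathy proliferative, Venous stasis retinopathy, Vitrectomy, Scintillating scotoma, Vision blurred, Visual impairment". A note says the list was built for MedDRA 25.0 and will be moved to the version in use at final database lock. It does not promise a review of which terms belong.

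SAP 4.6.5.17 uses the list twice:

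- It drives a descriptive table: "A summary of TEAEs suspected of worsening retinopathy (Section 6.6) and a summary of the results of the follow-up dilated fundoscopic exam". The first summary takes every listed term, with no severity filter.
- It supplies one route to AESI: "severe/serious adverse events from the PTs defined in searching criteria in Appendix 6.6 (Section 6.6) will be considered as AESI and summarized".

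A further AESI route does not use the list. A case qualifies if fundoscopy is repeated on clinical suspicion and shows de novo or progressed retinopathy.

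On reporting, Protocol 10.4.1 says of medical and surgical procedures that "the condition that leads to the procedure is the AE". Protocol 10.4.4 asks that, whenever possible, the diagnosis be recorded and not its separate signs and symptoms.

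**The concern.** With a closed list, a term that is not on it is not found. Other topics in SAP 6.6, such as hepatic events, hypersensitivity and arrhythmias, are searched by standardised queries or high-level terms, which bring in related terms as a group. The retinopathy list has no such safety net.

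The gap is odd given what the list does contain. It includes an operation on the vitreous, two terms for retinal bleeding, and mild or non-specific complaints such as blurred vision and diplopia, but not bleeding into the vitreous itself. At stake is whether the trial's dedicated retinopathy table, for a protocol-named AESI in a type 2 diabetes population, shows an event that a reader would expect to find there.

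**Working it through.** No power or alpha calculation applies, and the plan gives no figure to reproduce. The check is a count of the printed list, followed by a reading of how it is used.

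**1. Content of the list (SAP 6.6).** Split at the commas, it has 59 terms, all distinct. A text search gives:

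| Search string | Matches | Terms |
|---|---|---|
| vitr | 1 | Vitrectomy |
| haem | 2 | Retinal haemorrhage; Retinopathy haemorrhagic |
| hem, bleed | 0 | none |
| fundo | 2 | Fundoscopy; Fundoscopy abnormal |

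Vitreous haemorrhage terms: 0.

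**2. Could a neighbouring term pick the event up?** Take a vitreous haemorrhage treated by vitrectomy and noticed as blurred vision.

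- Protocol 10.4.1 places procedures among the things that do not meet the AE definition and makes the underlying condition the event. Vitrectomy should not be the reported term.
- Protocol 10.4.4 prefers the diagnosis to its symptoms. Vision blurred or Sudden visual loss should not be reported once the diagnosis is known.

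A site that follows both rules reports the haemorrhage alone. That report matches none of the 59 terms, provided MedDRA codes it to a term of its own.

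**3. Effect on each output.**

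| Output | Depends on the list? | Event coded only to vitreous haemorrhage |
|---|---|---|
| Summary of TEAEs suspected of worsening retinopathy (SAP 4.6.5.17) | Yes | Absent |
| AESI by severe/serious listed term (SAP 4.6.5.17) | Yes | Not found |
| AESI by repeat fundoscopy (SAP 4.6.5.17) | No | Found if an examination records de novo or progressed retinopathy |
| TEAEs by preferred term within system organ class (SAP 4.6.2.1) | No | Shown if treatment-emergent |
| SAE table and listing (SAP 4.6.3.2), narrative (SAP 4.6.4) | No | Shown if serious |

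The AESI sentence in SAP 4.6.5.17 joins its two conditions with a plain conjunction. The table reads them as alternatives, which is the natural sense.

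**4. The bare term Fundoscopy.** The rule in step 2 applies here too: an examination is a procedure and should not be reported as an event, and its results go to a dedicated eCRF page (Protocol 8.3.2.16). If one were misreported as an event, it would enter the unfiltered TEAE summary whatever it showed. It would reach AESI by the list only if also severe or serious.

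**The case against.** A reader might infer that a serious vitreous bleed will be missing from the AESI data. The documents do not support that. Protocol 8.3.2.16 calls for a follow-up dilated examination after any AE suspected of worsening retinopathy and does not tie this to the SAP list. If that examination records new or progressed retinopathy, the case becomes an AESI without any listed term. This stands and limits the point. It is not a full answer: no post-baseline examination is scheduled for everyone, the route depends on what the examination records, and it does nothing for the list-based TEAE summary.

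A reader might also infer that a routine fundoscopy counts as a retinopathy complication. It does not. The reporting rule keeps a bare examination out of the AE data, and the list route to AESI is confined to severe or serious events.

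Three further objections are fair:

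- No serious event disappears from the report, and no type I error-controlled endpoint is touched.
- Exclusion criterion 10 (Protocol 5.2) removes people with a history of proliferative retinopathy, macular edema, or nonproliferative retinopathy requiring acute treatment, confirmed by a dilated examination before randomization. Such events may therefore be few, although new disease during 72 weeks is not ruled out.
- Neither document mentions vitreous haemorrhage or reproduces MedDRA. That it has its own preferred term, and would not be coded to a listed one, must be checked in the dictionary.

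**Conclusion.** The point holds in a limited form. The list has no vitreous haemorrhage term, and the protocol's own reporting rules mean that Vitrectomy and the symptom terms cannot be relied on to fill the gap. An event coded only to vitreous haemorrhage would be absent from the TEAE summary in SAP 4.6.5.17. It would not be found by the preferred-term route to AESI and would reach AESI status only through a repeat fundoscopy showing de novo or progressed retinopathy. If serious, it remains visible in the SAE table and listing.

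The size cannot be expressed as a percentage of events lost: the documents give no rate for retinopathy complications and no basis for estimating how many would be vitreous bleeds. The conclusion assumes that vitreous haemorrhage is a separate preferred term in the MedDRA version used, that sites report as the protocol asks, and that the two AESI conditions are alternatives. The Fundoscopy term is a minor matter affecting the TEAE summary alone, and only if an examination is misreported as an event.

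**What to change.** Add Vitreous haemorrhage to the diabetic retinopathy list in SAP 6.6, after confirming the exact preferred term in the MedDRA version used at database lock. The update for that version, already planned, is a convenient time to do it.

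Optionally, drop the bare term Fundoscopy and keep Fundoscopy abnormal, which already covers examinations with a finding.

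The cost is a wording change in the SAP and a matching update of the search list. No new data, protocol amendment or change to site procedures is needed.

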8.3.2.15. Metabolic Acidosis, Including Diabetic Ketoacidosis

Ketoacidosis, a serious life-threatening condition requiring urgent hospitalization, has been reported rarely in patients with T2DM. Participants who present with signs and symptoms consistent with severe metabolic acidosis should be assessed for ketoacidosis regardless of presenting BG levels, as ketoacidosis may be present even if BG levels are less than 250 mg/dL. If ketoacidosis is suspected, SGLT-2 inhibitor should be discontinued (if used), patients should be evaluated, and prompt treatment should be instituted. Treatment of ketoacidosis will require insulin, and carbohydrate replacement.

Lactic acidosis is a risk for participants with T2DM who excessively drink alcohol, have impaired kidney function (eGFR <30 ml/min/m²), and are on metformin therapy. Routine bicarbonate assessment will be performed during the course of the study. If lactic acidosis is

suspected, metformin should temporarily be discontinued (if used) until the resolution of the event.

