4.6.5.18. Metabolic Acidosis

Severe/serious treatment-emergent metabolic acidosis, including diabetic ketoacidosis, will be captured as an AESI.

The counts and percentages of participants with metabolic acidosis, including diabetic ketoacidosis, may be summarized by treatment based on searching criteria in Appendix 6.6 (Section 6.6).

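### The SAP's search list for the metabolic acidosis AESI contains no general acidosis term, so an event coded under the topic's own name would be left out of the AESI count

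*SAP*

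**What the plan says.** Protocol 9.4.4.3 lists the AESI as "Metabolic acidosis, including diabetic ketoacidosis". Protocol 8.3.2.15 treats acidosis as the wider presentation and ketoacidosis as one cause to look for: "Participants who present with signs and symptoms consistent with severe metabolic acidosis should be assessed for ketoacidosis regardless of presenting BG levels". The same section also discusses lactic acidosis and plans routine bicarbonate measurement.

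SAP 4.6.5.18 keeps the protocol's topic and adds a severity condition: "Severe/serious treatment-emergent metabolic acidosis, including diabetic ketoacidosis, will be captured as an AESI". It goes on to say that counts and percentages of participants with the topic "may be summarized by treatment based on searching criteria in Appendix 6.6 (Section 6.6". That second sentence states no severity condition.

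SAP Appendix 6.6 supplies the search rule: "Metabolic acidosis including diabetic ketoacidosis will be identified using the following MedDRA PTs". The list has 13 entries. The only acidosis on it that is not a ketoacidosis is "Lactic acidosis". Several entries are laboratory findings, such as "Blood ketone body increased".

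**The concern.** The topic and the search do not match. The word *including* in both documents makes ketoacidosis a subset of metabolic acidosis, but the search covers ketoacidosis, lactic acidosis and ketone findings, and leaves out the parent term.

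A report under the parent term is easy to foresee. Protocol 10.4.4 asks investigators to record a diagnosis rather than signs and symptoms whenever possible. Bicarbonate is in the chemistry panel (Protocol 10.2). A site that finds acidosis, assesses for ketoacidosis as 8.3.2.15 requires and excludes it could well report metabolic acidosis without further qualification. Under the rule as written, that event is not in the AESI count even if it is serious.

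At stake is the accuracy of one AESI statement. The study report could state that no metabolic acidosis AESI occurred while its own serious adverse event table shows an event of that name.

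**Working it through.** The plan gives no figure to reproduce here. The check is a count of the list and a search for any clause that would widen it.

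**1. The list (SAP Appendix 6.6), grouped**

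| Group | Terms | Count |
|---|---|---|
| Ketoacidosis | Ketoacidosis; Diabetic ketoacidosis; Euglycaemic diabetic ketoacidosis; Diabetic ketoacidotic hyperglycaemic coma | 4 |
| Other named acidosis | Lactic acidosis | 1 |
| Ketosis or ketone finding | Ketosis; Diabetic ketosis; Ketonuria; Blood ketone body; Blood ketone body increased; Blood ketone body present; Urine ketone body; Urine ketone body present | 8 |
| General acidosis (*Metabolic acidosis*, *Acidosis*) | none | 0 |

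Total: 4 + 1 + 8 + 0 = 13.

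**2. Is there a clause that widens the list?**

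- The acidosis entry cites no Standardised MedDRA Query, no High Level Term and no wording for other related terms. Most other topics in the appendix use such queries or High Level Terms.
- A version note appears elsewhere in the appendix: "This table was developed for MedDRA version 25.0 and will be updated to the version of MedDRA to be used at the time of the" (cut here; the sentence ends by naming the database lock). It closes the diabetic retinopathy list and refers to that table. It promises a version update, not new terms, and does not reach the acidosis list.
- SAP 4.9, on changes to protocol-planned analyses, does not record a narrowing of the topic to ketoacidosis.

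**3. What the rule does to an event coded *Metabolic acidosis***

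| Display | Event included? |
|---|---|
| AESI count (4.6.5.18, terms from Appendix 6.6) | No, even if severe or serious |
| Special-topic summary (4.6.5.18) | No, at any severity |
| General treatment-emergent tables by PT (4.6.2.1) | Yes |
| Serious adverse event table and listing (4.6.3.2) | Yes, if serious |
| Patient narrative (4.6.4) | Yes, if serious |

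**4. The coding assumption.** The documents do not show that *Metabolic acidosis* and *Acidosis* are PTs. If they are, and the event is coded to one of them, the list retrieves none of these events. If the reported wording is instead coded to one of the 13 listed PTs, the event is retrieved. Whatever is coded outside the 13 is not.

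**The case against.** The best defence is that little is lost. Protocol 8.3.2.15 describes two specific forms, ketoacidosis and lactic acidosis, and both are on the list. The metformin and low-eGFR risk in that section relates to lactic acidosis, and the note to exclusion 15 further restricts metformin users by renal function. Acidosis that accompanies acute renal failure or dehydration may reach AESI status through SAP 4.6.5.11.1 or 4.6.5.11.2, provided that the renal or dehydration event is itself reported and is severe or serious. Laboratory shift tables and abnormal-value listings (4.6.3.6) cover bicarbonate. The special-topic summary is worded only as something that may be done.

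Most of this stands, and it limits the consequence. It does not close the gap. The other routes capture a companion event or show the case in a different table; none puts a metabolic acidosis event into the metabolic acidosis AESI count.

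A reader might also infer that the eight ketone terms inflate the topic, for example through diet-induced ketosis that is more frequent on tirzepatide. The documents do not support this. No ketone test is scheduled (Protocol 10.2), and an abnormal laboratory result becomes an adverse event only if judged clinically significant (Protocol 10.4.1). Nothing in either document says that the study diet produces ketosis or that one arm would show more of it. The AESI is restricted to severe or serious events, and SAP 4.6.5 displays special topics by PT, so a ketone-only case would be visible as such. A wide screen also fits the appendix's style elsewhere, as in the broad hepatic queries.

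**Conclusion.** The point holds as a mismatch between a named AESI and its search list. Its size is 0 of 13 terms for general acidosis, so the rule finds none of the events coded to *Metabolic acidosis* or *Acidosis*, on the assumption that these are PTs in the version used. Neither document gives an expected rate for such events, so the number affected cannot be estimated.

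Two stronger readings should be resisted. One is that such an event would be lost from the report: it is missing from the AESI count and the special-topic summary, not from the general or serious adverse event displays. The other is that the 8 ketone terms out of 13 measure misclassification: that is a share of listed terms and says nothing about the share of events.

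The consequence is confined to safety reporting on one topic. No hypothesis test, error rate or efficacy estimate depends on it. The correction is still worth making before database lock, because the AESI display exists so that readers need not rebuild the count from the general tables.

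**What to change.** In SAP Appendix 6.6, add to the metabolic acidosis entry the general acidosis PTs available in the MedDRA version used at database lock (*Metabolic acidosis* and *Acidosis*, if present as PTs, and any comparable terms), so that the search matches the topic named in Protocol 9.4.4.3 and SAP 4.6.5.18. State that the list will be checked against that version.

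Keep the ketosis and ketone terms as a sensitive screen. Because the display is already by PT, a separate subtotal for them is optional.

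The cost is an edit to one SAP list and a longer term list in one table program. No new data are needed and no other analysis changes.
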